### **Population**

The source population for this study will be all patients contributing data to the GloBE-Reg registry and who are treated with either long acting Ngenla (somatrogon) or daily hGH Genotropin (somatropin) at the discretion of the prescribing physician. Participants can be located anywhere in the world. Participants will be followed for up to 10 years until the end of the study or one of the following occurs: withdrawal of consent, discontinuation of either Ngenla (somatrogon) or

PFIZER CONFIDENTIAL

CT24-WI-GL02-RF02 7.0 *Non-Interventional Study Protocol Template For Secondary Data Collection Study*

Page 12 of 63

090177e1a57a0182\Approved\Approved On: 16-Feb-2026 13:43 (GMT)

Genotropin (somatropin), discontinuation from the GloBE-Reg registry, lost to follow up or death. The registry is growing and additional centers around the world are expected to be included over the course of the study period.

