### 8.2. Setting

The source population for this study will be the subset of patients contributing data to the GloBE-Reg registry who are treated with either long acting Ngenla (somatrogon) or daily hGH Genotropin (somatropin) at the discretion of the prescribing physician. This population is thought to be a representative sample of children treated with Ngenla (somatrogon) and Genotropin (somatropin) across the world. Data will be included from eligible participants of any age who meet the study criteria and who receive care at centers enrolled in GloBE-Reg that have agreed to share their data with Pfizer during the data collection period. The registry is growing and additional centers around the world are expected to be included over the course of the study period.

The data collection period is from September 30, 2025 to August 31, 2035. No sampling will be performed. Participants can be located anywhere in the world and will be followed up to 10 years until the end of the study or one of the following occurs: withdrawal of consent, discontinuation of

either Ngenla (somatrogon) or Genotropin (somatropin), discontinuation from the GloBE-Reg registry, lost to follow up or death.

The treating physician will follow patients treated with Genotropin (somatropin) or Ngenla (somatrogon) as per routine clinical practice and will collect and enter relevant patient data as part of the defined minimum data set collected by the GloBE-Reg registry.

During the study, duration of treatment exposed will be defined as:

Genotropin/Ngenla: (last dose date – baseline date + 1)/365.25,

where baseline date is the initial visit date on the Reported Outcomes eCRF form.

The data collected via GloBE-Reg will be de-identified and sent to Pfizer for analysis. Pfizer will analyze the data to evaluate treatment effectiveness, safety, adherence and compliance.

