**Repeated Measures**

This model will only be performed with those patients without treatment switch until a given time point. Continuous variables will be analyzed by a Mixed Model for Repeated Measures (MMRM) under the MAR framework, including all post baseline timepoints data as outcome variables and baseline data as a covariate including the relevant patient/disease characteristics. Repeated time variable will be modeled as a continuous variable and treatment (Genotropin versus Ngenla) as a class variable with an unstructured covariance and least square means along with 95% CI will be presented.

The adjusted mean changes from Baseline at Month 6, 12, 18, 24, etc., for each treatment group will be estimated in the framework of this model, as well as the between group differences and the 95% CIs for the adjusted mean, when applicable.

The MMRM model will be implemented using SAS® (version 9.4 or higher) generalized linear mixed procedure (PROC MIXED) with an unstructured correlation matrix to model the within-patient errors. If this model does not converge, a heterogeneous Toeplitz covariance structure followed by the

090177e1a57a0182\Approved\Approved On: 16-Feb-2026 13:43 (GMT)

heterogeneous first-order autoregressive covariance structure will be considered. Parameters will be estimated using the Newton-Raphson algorithm. Denominator degrees of freedom will be estimated using the Kenward-Roger approximation.

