### **Longitudinal Model/Sensitivity Analysis**

To assess the longitudinal association between outcomes and time-varying treatment (*i.e.* patients switch treatment from Genotropin to Ngenla or vice versa at any time-point), a propensity model approach will be applied to calculate the inverse probability of treatment weights (IPTW). This model is assumed to control for time-varying confounding when time-varying treatments are used in longitudinal analyses.

The IPTW will be calculated using propensity score model in which the choice of the treatment at each visit will be considered as the outcome (Genotropin vs Ngenla) and the pre-specified baseline characteristics (See Table 9-3 Model Covariates) as independent variables. Once IPTWs per patient are derived, the models described in the Repeated Measure model will be applied with the weights. The models will include treatment group (time-varying covariate), time (in years) and IPTW. This approach will be considered as a sensitivity analysis *to assess the impact of treatment switching*.

Detailed methodology for summary and statistical analyses of data collected in this study will be documented in a statistical analysis plan (SAP), which will be dated, filed, and maintained by the sponsor. The SAP may modify the plans outlined in the protocol; any major modifications of primary endpoint definitions or their analyses would be reflected in a protocol amendment.

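### The rule ending follow-up at discontinuation of either drug conflicts with the planned switching analysis, and the primary MMRM does not say whether switchers' earlier visits are kept

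*Protocol*

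**What the plan says.** **Follow-up.** Protocol section 8.2 (Setting) says that participants "will be followed up to 10 years until the end of the study or one of the following occurs: withdrawal of consent, discontinuation of" and, continuing over the page, "either Ngenla (somatrogon) or Genotropin (somatropin), discontinuation from the GloBE-Reg registry, lost to follow up or death". The Population paragraph of the abstract has the same rule: "withdrawal of consent, discontinuation of either Ngenla (somatrogon) or", continuing "Genotropin (somatropin), discontinuation from the GloBE-Reg registry, lost to follow up or death". In both places, leaving the registry is a separate item from discontinuing a drug. Neither place mentions a patient who changes from one study drug to the other.

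**Primary model.** Section 8.7, Repeated Measures: "This model will only be performed with those patients without treatment switch until a given time point". The next sentence reads: "Continuous variables will be analyzed by a Mixed Model for Repeated Measures (MMRM) under the MAR framework, including all post baseline timepoints data". Adjusted means and between-drug differences are wanted at six-month steps.

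**Switching analysis.** Section 8.7, Longitudinal Model/Sensitivity Analysis, covers the case where "patients switch treatment from Genotropin to Ngenla or vice versa at any time-point". It specifies: "The models will include treatment group (time-varying covariate), time (in years) and IPTW". Its stated purpose is to gauge the effect of switching.

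**Other inputs.** Section 8.5 expects at least 2000 Genotropin and 700 Ngenla participants. The protocol gives no switching rate and no reasons for switching. The exposure variables in section 8.3 record why therapy was stopped; the options include lack of efficacy, adverse events, the patient's own choice and attainment of final height.

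**The concern.** There are two linked problems.

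First, a patient who moves from Genotropin to Ngenla has discontinued Genotropin. Taken at its word, section 8.2 ends that patient's follow-up at the switch. A model with time-varying treatment learns about switching from visits after the switch. One section therefore closes the record at the point where another needs it to continue. At stake is the only analysis in the plan aimed at switching.

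Second, being unswitched at a given time point is a post-baseline condition. If the restriction means that a switcher is left out altogether for that time point, the drugs are compared among patients selected by what happened after baseline. A likelihood analysis under MAR can handle switching that depends on earlier observed outcomes, but only if those earlier outcomes are in the model. Dropping them gives up the protection that the same paragraph invokes. At stake is a possible bias in the primary comparison.

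**Working it through.** **1. The texts side by side.**

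| Place | What it fixes | Consequence for a switcher |
|---|---|---|
| 8.2 and abstract | Discontinuing either drug ends follow-up; no exception | Literal reading: no visits after the switch |
| 8.7, Longitudinal Model | Treatment varies over time; switches in both directions | Visits after the switch are needed |
| 8.7, Repeated Measures | Only patients not switched by the time point | Earlier visits kept or dropped: not stated |

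The first two rows cannot both be followed as written. The third row allows two readings: (a) the switcher is dropped for that time point, or (b) the visits before the switch are kept and later ones are treated as missing.

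**2. Yardstick.** The protocol states no power, effect size or SD, so there is no figure of its own to reproduce. In SD units, with the group sizes from section 8.5, an unadjusted comparison at one time point with everyone contributing has the 95% CI half-width

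1.96 × √(1/2000 + 1/700) = 1.96 × √0.0019286 = 0.086 SD.

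**3. Illustrative simulation.** Every setting here is an assumption; none comes from the protocol. There were two visits, a standard normal outcome, correlation 0.6 between visits, a true between-drug difference of 0 and 1,000,000 patients per arm. The switch happens between the visits with probability 1/(1 + exp(−(m − s·L))), where m is solved to give the target switching rate. The slope s is 0, 0.5 or 1.0 per SD of poorer response. L is either the observed first-visit outcome or the unobserved second-visit outcome. The estimates of the second-visit mean in an arm are:

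- Reading (a): the mean of y₂ in non-switchers.
- Reading (b): the mean of y₂ in non-switchers + b × (mean y₁ in all − mean y₁ in non-switchers), with b the slope of y₂ on y₁ in non-switchers. This is the likelihood estimate under MAR with the earlier visit kept.

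Spurious Ngenla-minus-Genotropin difference in SD, as (a) / (b), by switching rate (Genotropin/Ngenla):

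| Switching depends on | 10%/5% | 30%/5% | 50%/10% | 20%/20% |
|---|---|---|---|---|
| Nothing | 0.000 / −0.001 | 0.000 / 0.000 | 0.002 / 0.003 | 0.002 / 0.002 |
| Observed, s = 0.5 | −0.015 / 0.000 | −0.072 / −0.002 | −0.114 / −0.003 | 0.000 / −0.001 |
| Observed, s = 1.0 | −0.029 / −0.002 | −0.125 / −0.002 | −0.193 / 0.001 | 0.002 / 0.002 |
| Unobserved, s = 0.5 | −0.024 / −0.015 | −0.118 / −0.077 | −0.187 / −0.120 | −0.002 / −0.002 |
| Unobserved, s = 1.0 | −0.043 / −0.028 | −0.208 / −0.141 | −0.322 / −0.222 | 0.001 / 0.001 |

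Differences of up to about 0.003 are simulation noise.

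**4. Direction.** If good responders leave instead (30%/5%, s = 0.5, observed response), reading (a) lowers the Genotropin mean by 0.086 SD and the Ngenla mean by 0.014 SD. The spurious difference is then −0.014 − (−0.086) = +0.072 SD, the opposite sign. Reading (b) again gives about 0. With 20% switching in both arms the difference is about 0, although under (a) response-dependent switching (poorer responders leaving) raises each arm's mean by 0.06 to 0.17 SD.

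**The case against.** The strongest reply is that the plan is clear in intent. Discontinuation of either drug can be read as stopping study treatment altogether. A switched patient still meets the first inclusion criterion, and the longitudinal model shows that post-switch visits were expected. Likewise, the primary model is a single MMRM under MAR using all post-baseline time points, so contributing until the switch is a natural reading, and on that reading the simulated bias from observed response vanishes. Detailed methodology is left to the SAP.

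Much of this stands. A reader might infer that the post-switch data will be missing and the sensitivity analysis cannot be run. The protocol does not establish that; it establishes two statements that conflict when taken literally. The follow-up rule is fixed in the protocol itself, twice, so the protocol is where it has to be corrected. The primary-model sentence is ambiguous rather than wrong.

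A reader might also infer that the primary analysis selects good responders and flatters Genotropin. Nothing in the protocol says that patients switch because of poor growth. The recorded reasons for stopping are mixed, and the background stresses injection burden, which need not track response. With switching unrelated to response there is no bias, and with good responders leaving the sign reverses.

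Finally, a reader might want follow-up for safety after treatment ends. The secondary objective concerns rates among participants on the drugs, and time at risk is defined as exposure time. That is a coherent on-treatment choice, and preferring another is not an error in the plan.

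**Conclusion.** The conflict between the follow-up rule (section 8.2 and abstract) and the time-varying switching analysis (section 8.7) is real on the literal text and must be reconciled. The restriction on the primary MMRM is a conditional concern. If it drops switchers' earlier visits, it conditions on a post-baseline event and may bias the comparison in a direction that cannot be foreseen.

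For size, under the assumed settings with switching dependent on observed response, the spurious difference is up to about 0.19 SD if switchers are dropped and about 0 if their pre-switch visits are kept. The expected half-width is 0.086 SD. The bias could therefore exceed the sampling uncertainty, but it is also near 0 when switching is unrelated to response or is alike in both arms. If switching depends on unobserved current response, keeping the earlier visits reduces the bias without removing it: 0.222 against 0.322 SD in the worst case run.

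It is tempting to set these figures against the pivotal-trial difference in height velocity in section 6 (10.10 − 9.78 = 0.32 cm/year). The documents do not support that: they give no SD for height velocity with which to convert, and an error in one arm's mean is not a between-arm difference.

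**What to change.** - **Section 8.2 and abstract (Population):** state that a change between the two study drugs does not end follow-up. The rule for patients who stop both can stay as it is.
- **Section 8.7, Repeated Measures:** replace the restriction on patients with an analysis-level censoring date. Every patient contributes all visits up to the switch, and later visits are set to missing.
- **Section 8.7, Longitudinal Model:** state that visits after the switch are used in the weighted analysis.

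The cost is wording in the abstract, 8.2 and 8.7, made through a protocol amendment with the ethics approval that section 9.4 requires. A switched patient is still treated with one of the two study drugs, so remains within the data the sponsor already plans to receive.

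Two limits remain. Keeping pre-switch visits does not remove bias from switching that depends on unobserved response. The weights in section 8.7 are built from baseline characteristics, so the weighted analysis would not adjust for interim growth or IGF-I as drivers of switching, even with the post-switch visits in hand.

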#### Rationale and background

Human growth hormone (hGH) is a 191-amino-acid pituitary protein that stimulates production and release of insulin-like growth factor-I (IGF-I). Growth hormone (GH) and IGF-I are the primary mediators of the promotion of growth in children and play a role in the regulation of body composition and metabolism in children and adults. Growth hormone deficiency (GHD) results in inadequate levels of GH and IGF-I, which subsequently results in abnormal linear growth in children. Children with GHD have been treated with daily administration of recombinant hGH replacement therapy for many years which has been proven to be safe and effective.

Recombinant hGH has also been approved in many countries around the world for other conditions associated with growth failure and/or abnormal body composition. Children with GHD, Turner Syndrome (TS), Small for Gestational Age (SGA) and Idiopathic Short Stature (ISS) have been treated with daily administration of recombinant hGH replacement therapy for many years. Children with Prader-Willi syndrome (PWS) have also been treated with hGH for both the associated growth failure and abnormal body composition.

The burden of daily administration may cause sub-optimal adherence and limit the therapeutic utility of existing formulations of recombinant hGH. Ngenla (somatrogon) is a long-acting, once-weekly subcutaneously administered form of hGH, currently approved in many countries around the world for use as a long-term treatment in children with growth failure due to an inadequate secretion of endogenous GH.

PROGRES 2.0 is a multi-country, non-interventional, observational cohort study with the objective to assess the long-term effectiveness and safety of both Genotropin (somatropin) and Ngenla (somatrogon), at the discretion of the treating physician in routine clinical practice. This study will obtain real world data as a sub-study of the Global Registry for Novel Therapies in Rare Bone and Endocrine Conditions (GloBE-Reg). GloBE-Reg is an international registry project that obtains data on effectiveness and long-term safety through the collection of real-world data on all available forms of growth hormone and supports sub-studies focusing on various aspects of interest to treating

090177e1a57a0182\Approved\Approved On: 16-Feb-2026 13:43 (GMT)

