The sub-optimal adherence with daily hGH is well established, as is the burden of daily injections for both participants and caregivers. Long-acting hGH may obviate the need for the majority of injections currently required in daily hGH products. As demonstrated in animal models and clinical studies, Ngenla may be injected once per week resulting in similar clinical efficacy as daily injections of hGH. In the pivotal global Phase III clinical trial, the primary objective of non-inferiority (clinical comparability) for weekly Ngenla compared to daily hGH was met (annualized height velocity (HV) at Month 12 for once-weekly Ngenla was 10.10 cm/year versus 9.78 cm/year for daily hGH). Low numbers of serious adverse events (SAEs) were reported in both the weekly Ngenla and daily hGH groups, and the majority of adverse events (AEs) were of mild to moderate severity. Thus, weekly Ngenla administration was generally well-tolerated in pediatric participants.

The purpose of the Pfizer Registry of Outcomes in Growth hormone REsearch (PROGRES) 2.0 study will be to address the identified need for long-term effectiveness and safety data on the use of Ngenla (somatrogon) and Genotropin to reflect outcomes that occur in real-world clinical practice.

This noninterventional study is designated as a PASS and is conducted voluntarily by Pfizer.

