## 8. RESEARCH METHODS

### 8.1. Study Design

This is a multi-country, non-interventional, observational cohort study to assess the long-term effectiveness and safety of both a daily hGH Genotropin (somatropin) and a long-acting hGH Ngenla (somatrogon), at the discretion of the treating physician according to routine clinical care in a real-world setting.

The study will obtain data collected by the GloBE-Reg registry via a minimum data set, which was developed by an expert working group for monitoring the effectiveness and safety of both daily and long-acting GH in childhood GHD.

This study will have a broad geographic reach, including and participating centers are typically underrepresented in global studies. This will enable the evaluation of key primary and secondary endpoints, including the primary outcomes of interest: height, IGF-I, BMI, and bone age and secondary outcomes of interest: injection site reactions, immunogenicity and adherence. The longitudinal nature of the data will allow the evaluation of effectiveness and safety of Ngenla (somatrogon) and Genotropin (somatropin) and the endpoints will be evaluated within numerous prespecified strata or subgroups.

To evaluate the effectiveness and safety of Ngenla and Genotropin within the study population, participants will be stratified by select *a priori* subgroups, including but not limited to: age, sex, puberty status, follow-up time, medical comorbidities, initial disease/treatment indications, peak GH levels, diagnosis for GH disorder, and study region (Europe, Japan, North America, and Rest of the World [RoW]/country).

Strengths of this study design include the strong generalizability and external validity due to the large sample size from an international cohort of participants and the real-world clinical data that will be obtained.

All assessments described in this protocol are performed as part of normal clinical practice or standard practice guidelines for the participant's population and healthcare provider specialty in the countries where this non-interventional study is being conducted.

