**Analysis of the Secondary Endpoints:**

For secondary endpoints, safety events of interest, medication errors and efficacy measurements, descriptive statistics, counts and proportions, crude incidence rates (i.e., number of events per person years) with associated two-sided 95% confidence intervals will be calculated. Incidence rate is calculated as the number of individual events observed during the time at risk (exposure time), divided by the total number of patient-years at risk for the event, multiplied by 100.

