### **Count outcomes or Incidence Rate Ratio**

Poisson regression (or negative binomial regression if data presents overdispersion) will be used to estimate the incidence rate ratio (IRR) along with 95% Wald CI between Ngenla-treated patients and Genotropin-treated patients.

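### Ending exposure on the last dose date for both products leaves up to 6 days of the final Ngenla dosing interval, and any SAE there that stops treatment, outside time at risk; for Genotropin the gap is under one day.

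*Protocol*

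**What the plan says.** Section 8.2 (Setting) defines duration of exposure once for both products: "Genotropin/Ngenla: (last dose date – baseline date + 1)/365.25". It adds: "where baseline date is the initial visit date on the Reported Outcomes eCRF form". The added day is ordinary inclusive counting, so exposure ends on the last dose date itself.

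Section 8.7 (Analysis of the Secondary Endpoints) takes the incidence rate as the "number of individual events observed during the time at risk (exposure time), divided by the total number of patient-years at risk". The end of exposure therefore limits the numerator as well as the denominator.

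The second Table 8-7 (Overview of Safety Analysis) assigns an incidence rate (IR), incidence rate ratio (IRR) and hazard ratio (HR) to SAEs and to medication errors; non-serious events receive descriptive statistics only. The regression for count outcomes is meant to "estimate the incidence rate ratio (IRR) along with 95% Wald CI between Ngenla-treated patients and Genotropin-treated patients".

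The dosing intervals differ. The abstract states: "Ngenla (somatrogon) is a long-acting, once-weekly subcutaneously administered form of hGH". Section 8.1 describes Genotropin as a daily product. The protocol gives no product-specific extension and no risk window after the last dose. Section 8.2 also ends follow-up at discontinuation, so later follow-up does not recover the events.

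**The concern.** A rule in which the last dose covers one day suits a daily injection. Applied to a weekly injection, it declares the participant unexposed for the remaining 6 days of an interval that the dose was meant to cover.

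For participants who simply continue, this hardly matters, because events and person-time shrink together. It matters when an event between two doses is the reason that the next dose is not given. The last dose then precedes the event by up to 6 days on Ngenla, and the event is dated after exposure has ended. Suppose a participant has one Ngenla dose on the baseline date and a serious reaction two days later that ends treatment. That participant contributes one day at risk and no event.

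Events that end treatment are among those a safety study most needs to count. Here they are more likely to be dropped on one product than on the other, and the two products are then compared by IRR and HR.

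**Working it through.** **Inputs from the protocol.** Exposure formula (section 8.2); events restricted to exposure time (section 8.7); dosing intervals of 7 days and 1 day (abstract, sections 6 and 8.1); expected participants 700 Ngenla and 2000 Genotropin (section 8.5). The protocol gives no figure for this bias, so there is nothing to reproduce.

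**Assumptions, not in the protocol.** A share s of events stops treatment before the next dose; events are dated by onset and timing is uniform over the dosing interval; injections are given at clock hour h.

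**Days left out.** Calendar days of the interval minus the day counted: Ngenla 7 − 1 = 6; Genotropin 1 − 1 = 0, apart from the hours of the next day before its dose is due.

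**Person-time.** 700 × 6 / 365.25 = 11.5 patient-years. Per participant, 6 days is 1.6% of one year on treatment and 0.33% of five years.

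**Share of treatment-stopping events dated after the last dose date.** An interval starting at hour h runs to hour h + 168 (weekly) or h + 24 (daily), and the counted part ends at hour 24:

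- Ngenla: (144 + h)/168
- Genotropin: h/24

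| h | Ngenla | Genotropin |
|---|---|---|
| 0 (midnight) | 144/168 = 86% | 0% |
| 8 (morning) | 152/168 = 90% | 33% |
| 20 (evening) | 164/168 = 98% | 83% |

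**Effect on the IRR with equal true rates.** IRR ≈ [1 − s(144 + h)/168] / [1 − s·h/24].

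| s | h = 0 | h = 8 | h = 20 |
|---|---|---|---|
| 5% | 0.96 | 0.97 | 0.99 |
| 10% | 0.91 | 0.94 | 0.98 |
| 20% | 0.83 | 0.88 | 0.97 |

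For s = 10% and h = 8: (1 − 0.0905)/(1 − 0.0333) = 0.9095/0.9667 = 0.94.

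The Ngenla rate on its own, at s = 10%, is understated by 8.6% (h = 0) to 9.8% (h = 20). The ratio moves less because Genotropin also loses events unless h = 0.

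**Check.** A simulation with h = 0 (150,000 patients per arm, 3 years, true rate 5 per 100 patient-years in both arms) gave an IRR of 0.92 at s = 10%, against 0.91 from the formula. It counted 14% of the treatment-stopping Ngenla events, in line with 1/7. At s = 0 the IRR was 0.99, essentially unbiased.

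**The case against.** The strongest objection is that the recorded data may not support reasoning at the level of days. Section 8.3 lists only an assessment date for adverse events; an occurrence date is listed for medication errors. If events are placed by the date of a routine visit, a treatment-stopping event on either product can fall after the last dose, and a few extra days would recover little. Nor is a general last dose date listed. The exposure variables contain a therapy stop date, and a last-injection date appears only under IGF-I. If the stop date is what will be used, part or all of the gap may close. This stands as a limit on the size. It does not remove the point, because the protocol states the formula without saying which date feeds it.

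Second, section 8.3 leaves operational definitions to the SAP, where a risk window could be set. That is fair, but section 8.2 does not defer this definition; it fixes it.

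Third, the scope is narrow. Only SAEs and medication errors get an IRR or HR. A medication error arises from dosing, so the mechanism barely applies to it. Section 6 reports few SAEs in either group of the pivotal trial. All of this stands.

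Fourth, the safety objective is descriptive, and section 8.9 already concedes possible underestimation. That section attributes it to underreporting, misreporting and missing data. It does not mention a loss that differs by product because of the formula.

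A reader might also infer that these events are lost almost only on Ngenla, so that the IRR falls by the full 6/7 of s. The formula does not support this: a Genotropin event on the day after the last dose is excluded too. The full figure holds only for injection near midnight.

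**Conclusion.** The point holds. One inclusive last-dose formula, combined with counting events only inside exposure time, treats a weekly and a daily product unequally and favours Ngenla. With events dated by onset, the Ngenla SAE rate and the Ngenla/Genotropin IRR are biased downward. So is the HR if it censors at the same date, which the protocol does not spell out.

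The bias is likely to be modest. At s = 10% the IRR under equal true rates is about 0.91 to 0.98, and at s = 5% about 0.96 to 0.99. The share of SAEs that stop treatment, the injection time, the uniform timing and the dating of events are all assumed. If no event stops treatment, the rate is essentially unbiased, and the 11.5 patient-years of lost exposure are negligible in themselves.

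Two stronger readings should not be drawn. Reactions on the injection day are still counted, so immediate reactions are not lost. Non-serious reactions do not reach the IRR or HR, because the safety table gives them descriptive statistics only.

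**What to change.** In section 8.2, replace the single formula by a time at risk that runs through the day the next dose would have been due, for both products alike:

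- Ngenla: (last dose date + 7 − baseline date + 1)/365.25
- Genotropin: (last dose date + 1 − baseline date + 1)/365.25

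Cap the end date at the earliest of switch to the other product, death, consent withdrawal, discontinuation from the registry, loss to follow-up and data cut-off. Without the full cap, person-time in which no event can be observed would be added, and mostly to Ngenla. Extending Ngenla alone would leave next-day Genotropin events uncounted and create an imbalance in the other direction.

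Use the same end date for events and person-time in the IR, IRR and HR. State which recorded field supplies the last dose date, given that the exposure variables list only a therapy stop date, and which date places an adverse event in time.

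The cost is a few lines in section 8.2 and the matching SAP derivation. The window itself needs no new data. It adds at most 700 × 7/365.25 = 13.4 patient-years on Ngenla and 2000 × 1/365.25 = 5.5 on Genotropin. The downside is that event counts may rise slightly.
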